3.1 Main and secondary variables

- Gestational age, weight, length and head circumference at birth
- Sex
- Multiple gestation

- Gestational pathology (diabetes, preeclampsia, maternal sepsis, placental disease, in vitro fecundation)
- IUGR and degree of IUGR
- Inborn vs Outborn
- Apgar at 5 and 10 minutes
- Antenatal steroids
- Type of delivery (vaginal vs caesarean)
- Coriamnionitis
- Type of feed (breastfeeding, donor milk or formula)
- Duration of breastfeeding
- Necrotising enterocolitis, early and late-onset sepsis, mortality
- Antibiotic use beyond 48 hours of life
- Days of parenteral nutrition
- Days of enteral nutrition
- Days of invasive ventilation, days of non-invasive ventilation, days of oxygen
- Days of stay in intensive care
- Chronic lung disease
- Intraventricular haemorrhage (I-IV)
- Periventricular leukomalacia
- Cranial ultrasound result
- Retinopathy of prematurity
- Neurosensorial hearing loss
- Cerebral palsy
- Colic in early infancy
- Bayley score at 2 years of age
- MRI at 2-3 years of age
- Growth chart
- Moment of “catch-up”
- Childhood diseases (asthma, atopic skin, hospital admissions, allergy,...)
- Need for antibiotics or probiotics during childhood >48 hours
- Weight and height at the assessment
- WISC-V at 6 years
- CBCL 6-18 (Child Behaviour Checklist 6-18)
- BRIEF-2
- Mother tongue
- Parental age
- Cultural level of parents
- Ethnical origin
- Parents work
- Kind of family (single parent, ...)
- Social services requirements
- Need to attend early stimulation centre

4 Study design

Quasi-experimental, sequential, unicentric, cohort study with the performance of neuropsychological tests and biomarkers of neurodevelopment, inflammation, and intestinal permeability.

We estimate an initial phase of 2 years with a comparison at 6 years of age (4 years after start of trial).

5 Enrolment of participants

Infants born below 32 weeks gestational age and birth weight under 1500g cared for at BCNatal Hospital Clínic (tertiary neonatal unit) in Barcelona between January 2014 and December 2019. There will be a 12 month wash out period (year 2017) to alleviate cross contamination of probiotics.

Participants will be contacted via phone (parent/legal guardian) for those that consented to be included for a 6-year assessment and blood sampling. In those cases where contact via phone has not been possible, contact to reference Paediatrician will be sought.

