5.2 Exclusion criteria

All neonates presenting with suspected congenital anomalies, inborn errors of metabolism, or genetic defects will be excluded. Infants with a suspected syndrome, or who had suffered events beyond the neonatal period, not related to prematurity, that could entail impairment in neurodevelopment (severe cranioencephalic trauma, oncological process, meningitis, or exposure to toxic substances) will also be excluded.

6 Treatment and study calendar

Intervention

Daily dose of 6x10⁹ UFC Infloran® -Berne, Switzerland- (Bifidobacterium bifidum NCDO 2203 and Lactobacillus acidophilus NCDO 1748) from 7 days of life until reaching a postmenstrual age of 34 weeks or discharge. The probiotic mixture will be provided in capsules, opened, dissolved in water and given orally or via nasogastric tube, according to the feeding regime of each neonate (breast milk, donor milk or formula). Where concerns for NEC or LOS are present, probiotics will be stopped and reinstated once enteral feeds are recommenced.

Evaluation of effect of intervention

At 24 months corrected age there will be a Bayley-III scale test in an extensive examination performed by independent assessors, blinded to group allocation. After this evaluation, patients will be divided into four categories according to their degree of neurodevelopment: survival without neurodevelopment impairment (normal neurodevelopment), mild impairment, moderate impairment, or severe impairment²⁶. Mild impairment will be considered if they have muscle tone changes, impaired fine or gross motor coordination, Bayley scale score between 71-84, moderate behaviour disorders or mild visual

disability. Moderate impairment will be diagnosed when suffering from spastic diplegia, hemiplegia, seizures (non-febrile), Bayley scores between 50-70, severe behaviour disorders, moderate visual disability or mild-moderate hypoacusis. Severe impairment will be attributed to subjects with spastic quadriplegia, choreoathetosis, ataxia, Bayley score <50, blindness or severe hypoacusis.

Posteriorly, at 6 years of age, we will assess the presence of cerebral palsy, learning difficulties, behavioural disorders (autism spectrum, attention deficiency and hyperactivity disorder) and scores in the tests WISC-V, CBCL 6-18 and BRIEF-2. We will also perform a semi-structured interview to parents or legal guardians to determine the degree of impairment of the child, that might have not been previously included.

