On the other hand, at 6 years of age we will proceed to sampling of blood plasma for the study of different biomarkers related to neurodevelopment, inflammation, and intestinal permeability. We will analyse the following: NeuN, Doblecortina, GFAP, GDNF, Ki67, Nrf2, BDNF, NGF, neurotrophina-1 (NT-1), neurotrophina-3 (NT-3), neurotrophina-4 (NT-4), DYRK1A, HIF1 α , S100B i GSK3B. Regarding inflammation we will assess IL1B, IL6, IL8, IL10, IL12, TNF- α . We will finally determine presence of lipopolysaccharide in plasma with an ELISA.

7 Statistics

Considering an alpha risk of $\alpha = 0.05$ and a beta risk of $\beta = 0.2$ in a bilateral contrast, a minimum of 90 subjects in each group were required to detect a statistically significant difference between groups, where for the control group the proportion of some neurodevelopmental alteration was expected to be at least 0.4 and for the group treated with probiotics at least 0.2.

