7.2 Statistical analysis

IBM SPSS Statistics 27.0.1.0 will be used for the statistical analysis. Non-parametrical analysis with a double-sided Mann-Whitney U test will be calculated for all continuous variables, whilst for categorical variables the chi-square test will be applied. In all cases, 0.05 will be considered the threshold of statistical significance. The relative risk (RR) and 95% confidence intervals will be determined for dichotomous variables. When encountering significant differences, the number needed to treat (NNT) will be analysed.

8 Ethics

The study will be in accordance with the Declaration of Helsinki (Fortaleza Version, Brazil October 2013) and will follow the legal requirements to fulfil the Spanish Biomedical Law of 14/2007. All patients, parents or legal guardians will be sought for informed consent.

9 Data processing and confidentiality

Treatment, communication and cease of data of personal character will be following the EU Ruling 2016/679 of the European Parliament and the Counsel of 27th April 2016, referring to protection of physical people and the treatment of personal data and the free circulation of data, being legally binding on the 25th of May 2018. The legal base of use of data will be in accordance to this act, established in the article 9 of EU 2016/679 Ruling.

All collected data will be deidentified and allocated a specific code, that will not allow any recognition of participants. Only the main promotor and collaborators will have access to data and will be allowed to enter the clinical history of patients for the purpose of this study.

Only legal requirement of medical emergency will allow the disclosure of any data related to participants of the study.

There will, however, be access upon request of non-identified data to Health Authorities, Ethics Committee and authorised personnel, for the purpose of quality assessment and study evaluation. Nevertheless, this will follow the existing legal frame and always guaranteeing confidentiality.

If data is to leave the EU, whether it is to entities related to the Hospital where patient was cared for, or third healthcare parties or collaborators, data will be protected via contracts or other established mechanisms to comply with EU legal requirements to data protection.

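### The four ordered 24-month impairment grades fall under a chi-square rule that ignores their order, while the 90 per group belongs to a two-level outcome that the protocol does not tie to those grades

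*Protocol*

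**What the plan says.** Protocol section 6, under the evaluation of the intervention, states that after the Bayley-III examination at 24 months corrected age "patients will be divided into four categories according to their degree of neurodevelopment". The levels are no impairment, mild, moderate and severe. They are defined by Bayley score bands together with motor, seizure, behavioural, visual and hearing findings.

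Section 7 sizes the study on a two-level outcome: "a minimum of 90 subjects in each group were required". Among controls, "the proportion of some neurodevelopmental alteration was expected to be at least 0.4"; the corresponding figure under probiotics is 0.2. Alpha is 0.05 two-sided and beta is 0.2.

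Section 7.2 has two test rules. Continuous variables go to a two-sided Mann-Whitney test; for the rest, "whilst for categorical variables the chi-square test will be applied". It adds relative risk with a 95% confidence interval for dichotomous variables, and a number needed to treat where differences are significant. It names no ordinal or trend test.

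**The concern.** The grades run in one direction, and hypothesis 1 claims improvement. A Pearson chi-square on group by four grades treats the grades as labels. It asks whether the two distributions differ in any way, not whether children moved towards less impairment. Two things follow.

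- **Interpretation.** A significant result could reflect fewer mild cases together with more severe ones. Relative risk is planned only for dichotomous variables, so no directional effect measure accompanies the four-level comparison.
- **Power.** If the effect is a general shift towards better grades, a 3-df test spreads its sensitivity over patterns that nobody has hypothesised.

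The protocol also does not say which form of the outcome carries the main test, the four grades or the two-level version. Nor does it say that the two-level version means mild or worse.

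**Working it through.** **Inputs from the protocol.** Control 0.4, probiotic 0.2, two-sided alpha 0.05, power 0.80, 90 per group (section 7); four ordered grades (section 6). The protocol gives no split of impaired children over mild, moderate and severe, so every split below is an assumption.

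**1. Reproducing the 90 per group.** With mean proportion 0.3,

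n = [1.960 x sqrt(2 x 0.3 x 0.7) + 0.842 x sqrt(0.4 x 0.6 + 0.2 x 0.8)]² / 0.2² = (1.270 + 0.532)² / 0.04 = 81.2, so 82.

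With continuity correction: (81.2 / 4) x [1 + sqrt(1 + 4 / (81.2 x 0.2))]² = 90.95, so 91. The stated 90 is therefore consistent, to within one child, with a continuity-corrected comparison of two proportions.

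**2. Power of the two-level test at 90 per group.** The noncentrality is

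90 x [2 x 0.1² / 0.7 + 2 x 0.1² / 0.3] = 90 x (0.0286 + 0.0667) = 8.57.

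On 1 df the power is about Φ(sqrt(8.57) - 1.960) = Φ(0.968) = 83%. Simulation gives 84%, or 80% with continuity correction. The section 7 figure holds for this outcome.

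**3. Power of the four-level chi-square under a proportional reduction.** Suppose every impaired grade is halved. A grade with control proportion p has mean 0.75p and deviation 0.25p in each arm, so it contributes 2 x (0.25p)² / (0.75p) = p/6. Summed over the impaired grades this is 0.4/6 = 0.0667, whatever the split. The normal grade again adds 0.0286. The noncentrality is the same 8.57, but it is now tested on 3 df (critical value 7.81), and power is 69% (70% simulated). For 80% the 3-df test needs about 115 per group: 115 x 0.0952 = 10.95, which gives 80.2%.

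**4. Other patterns.** Simulated power in %, 90 per group, two-sided 0.05. Each row has 40,000 simulated trials, except the common-odds-ratio row with 20,000. The common odds ratio is (0.2/0.8) / (0.4/0.6) = 0.375.

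| Control v probiotic (normal/mild/moderate/severe, %) | Chi-square, 3 df | Mann-Whitney | Two-level chi-square |
|---|---|---|---|
| 60/24/11/5 v 80/12/5.5/2.5 (each grade halved) | 70 | 83 | 84 |
| 60/24/10/6 v 80/13.3/4.3/2.3 (common odds ratio) | 70 | 85 | 84-85 |
| 60/24/10/6 v 80/16/3/1 (larger fall in worse grades) | 80 | 89 | 84 |
| 60/24/10/6 v 80/18/1.5/0.5 (still larger fall in worse grades) | 91 | 91 | 84 |
| 60/24/10/6 v 80/4/10/6 (only mild cases fall) | 95 | 68 | 84 |
| No effect | 5 | 5 | 5 |

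**5. A mixed, adverse pattern.** Take 60/28/8/4 v 60/14/14/12, so that any impairment is 40% in both arms but moderate and severe cases rise. The 3-df chi-square is significant in about 74% of simulated trials, Mann-Whitney in 13% and the two-level test in 5%.

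**The case against.** A reader might infer that the study's stated 80% power drops to 70%. The documents do not support that. The 80% is attached to the two-level outcome, a 2 x 2 chi-square is the matching test for it, and its relative risk shows direction. No power claim is made for the four-level table, and nothing makes that table the main test. This part of the objection stands in full.

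It also stands that the two-level outcome is most naturally the complement of the first grade, and so a collapse of the same scale. The protocol leaves the reader to infer this. The Bayley score is listed as a variable in section 3.1 and, as a continuous variable, would go to Mann-Whitney, so direction is not ignored in the 24-month analysis as a whole. The grade, however, also counts motor, seizure, behavioural, visual and hearing findings that a score comparison does not carry.

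An ordered test is not always stronger. It is clearly weaker if only mild cases fall.

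One might extend the point to intraventricular haemorrhage, which section 3.1 lists with grades I-IV. The hypothesis and objectives speak of reducing it and of its incidence, which is a yes/no comparison, and no grade-by-grade test is announced. The extension is not supported.

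Finally, the handling of one graded outcome could be left to an analysis plan. Here, though, section 7.2 does state a rule that covers this outcome, and the rule fits it poorly.

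**Conclusion.** The point holds in a limited form. As written, section 7.2 sends an ordered 24-month grade to a test that ignores the order and can be significant for a pattern opposite to the hypothesis. The protocol also does not link the two-level outcome behind the 90 per group to the four grades.

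The sample size itself is sound for the two-level outcome (80% to 84% power). The loss to about 70%, against 83% for a rank test, arises only if the four-level grade is tested on 3 df and the reduction is spread proportionally over the grades. With a common odds ratio the gap is 70% against 85%. Because the split is unknown, the 3-df figure can lie anywhere from about 70% to 95%. The case for change therefore rests more on what the test answers than on any single power figure.

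**What to change.** In section 7.2, add two statements:

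1. Any impairment at 24 months (mild, moderate or severe), compared with the chi-square test and reported as a relative risk with 95% confidence interval, is the outcome to which the 90 per group applies.
2. The four-level 24-month grade is compared with a test that uses its order: either Mann-Whitney on the grade, or a proportional-odds model reporting a common odds ratio with 95% confidence interval. The chi-square test is kept for unordered categories and two-level variables.

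The choice between the two ordered analyses should be fixed before the data are examined. The cost is a few lines of text. No new data are needed, Mann-Whitney is already in the plan, and SPSS runs both. There are two small downsides: an ordered test loses power if the effect is confined to mild cases, and the common odds ratio needs a check that the shift is similar across grades. Showing the counts in all four grades by group lets a reader see either departure.

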5.1 Inclusion criteria

Extreme premature infants <32 weeks and <1500g, cared at BCNatal Hospital Clinic during years 2014-2019. Participants will have to survive beyond 7 days of life (moment where the probiotic intervention will be given). Recruitment will start from January 2014 and will last until December 2019.

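### Twins and other multiples are eligible and, on the natural reading of the sequential design, share a group, but the fixed tests, the relative-risk intervals and the 90 per group treat every infant as independent

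*Protocol*

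**What the plan says.** Section 5.1 takes in "Extreme premature infants <32 weeks and <1500g, cared at BCNatal Hospital Clinic during years 2014-2019", provided they survive beyond 7 days. Section 5.2 lists the exclusions, beginning with "All neonates presenting with suspected congenital anomalies, inborn errors of metabolism, or genetic defects will be excluded". Multiples are not among them, and no rule limits the analysis to one infant per pregnancy. Section 3.1 lists "Multiple gestation" as a study variable, so multiples are expected.

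Section 4 describes a "Quasi-experimental, sequential, unicentric, cohort study". Section 5 adds: "There will be a 12 month wash out period (year 2017) to alleviate cross contamination of probiotics".

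On analysis, section 7.2 states: "Non-parametrical analysis with a double-sided Mann-Whitney U test will be calculated for all continuous variables". It assigns chi-square to categorical variables, and then: "The relative risk (RR) and 95% confidence intervals will be determined for dichotomous variables". Every test is judged at 0.05. On size, section 7 gives "a minimum of 90 subjects in each group were required to detect a statistically significant difference between groups", for proportions of 0.4 and 0.2, two-sided alpha 0.05 and beta 0.2.

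**The concern.** Siblings from one pregnancy share gestational age, maternal disease, genes and home, so their neurodevelopmental scores are likely to be positively correlated. What that does to a comparison depends on whether siblings sit in the same group. The protocol does not say which years belong to which group. A sequential design with a wash-out year in the middle implies that group follows birth period, and then siblings fall together. This is an inference, but the natural one. Same-group siblings inflate the variance of the group difference, and a test that treats them as independent understates it. Had siblings been split between groups, the error would run the other way.

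Mann-Whitney is the most exposed procedure. It is fixed for the Bayley and WISC-V scores and for the more than 20 biomarkers in section 6 where these are measured on a continuous scale. Section 7.2 also calculates a number needed to treat wherever a difference is significant, so a false positive would be carried into a clinical-looking figure.

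**Working it through.** **The plan's own figure.** Inputs from section 7: 0.4 vs 0.2, two-sided alpha 0.05, power 0.80.

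- Pooled formula: n = [1.96·√(2·0.3·0.7) + 0.842·√(0.24 + 0.16)]² / 0.2² = (1.270 + 0.532)² / 0.04 ≈ 81.2, so 82.
- With continuity correction: (81.2/4)·[1 + √(1 + 4/(81.2·0.2))]² ≈ 90.9, so 91.
- Unpooled gives 79 and arcsine 81.

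The 90 is thus reproduced within rounding by the continuity-corrected formula for independent samples. None of these variants contains a design effect.

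**Assumptions, not in the protocol.** Three scenarios give the share of infants in complete twin pairs and the sibling correlation on the underlying continuous scale: low 20% / 0.3, middle 30% / 0.5, high 40% / 0.7. The binary intraclass correlation (ICC) comes from a bivariate-normal threshold at risks of 0.2 to 0.4.

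**Formulas.**

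- Binary design effect = 1 + share × ICC. High scenario: 1 + 0.4 × 0.490 = 1.196. The standard error is understated by 1 − 1/√1.196 = 8.6%, and a correct interval is √1.196 − 1 = 9.4% wider.
- Rank design effect = 1 + share × (6/π)·asin(r/2). High scenario: 1 + 0.4 × 0.683 = 1.273.
- Large-sample level of a nominal 5% test = 2·[1 − Φ(1.96/√design effect)]. For Mann-Whitney this gives about 5.7%, 6.7% and 8.2%, in line with the simulation below.

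**Results.** Simulation with 90 per group and 100,000 runs (50,000 for the row with incomplete pairs). Ranges cover risks of 0.2 to 0.4.

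| | No twins | Low | Middle | High |
|---|---|---|---|---|
| Binary ICC | – | 0.163-0.191 | 0.295-0.330 | 0.456-0.490 |
| Binary design effect | 1 | 1.033-1.038 | 1.088-1.099 | 1.182-1.196 |
| Standard error too small by | 0 | 1.6-1.9% | 4.2-4.6% | 8.0-8.6% |
| Rank design effect | 1 | 1.058 | 1.145 | 1.273 |
| Mann-Whitney type I error | 4.9% | 5.6% | 6.6% | 8.1% |
| Same, half of the pairs incomplete | – | 5.3% | 6.0% | 6.6% |
| Chi-square type I error, uncorrected | 4.7-5.2% | 5.1-5.7% | 5.9-6.4% | 7.1-7.6% |
| Chi-square type I error, continuity-corrected | 3.1-3.7% | 3.4-4.1% | 4.1-4.6% | 5.0-5.6% |
| Coverage of ordinary RR interval at RR 0.5 | 95.6% | 95.0% | 94.5% | 93.4% |
| Power 0.4 vs 0.2, planned chi-square, uncorrected | 84.2% | 83.7% | 82.8% | 82.1% |
| Power, planned chi-square, continuity-corrected | 80.2% | 79.7% | 79.0% | 78.1% |
| Power, cluster-robust log-RR test | 83.1% | 81.6% | 79.1% | 75.6% |

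An effective-sample-size formula agrees with the last row. With rounded ICCs of 0.16, 0.32 and 0.48 the design effects are 1.032, 1.096 and 1.192. The effective n is then 90/1.032 = 87.2, 90/1.096 = 82.1 and 90/1.192 = 75.5 per group, and power is 82.8%, 80.4% and 77.0%, against 83.9% under independence.

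**Does the remedy work?** In the same simulations, cluster-robust RR intervals cover 95.4%, 95.5% and 95.3%. A rank test with variance clustered by pregnancy has a type I error of 5.3% in all three scenarios.

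**The case against.** The strongest case against runs as follows.

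- **The sized endpoint is hardly touched.** The 90 is closest to the continuity-corrected formula, and that version of chi-square stays at 3.4-5.6% in every scenario. This stands, with a reservation: section 7.2 does not name the version, and 82 raised by 10% also gives about 90 (82 × 1.1 = 90.2), so the match does not settle which test was meant.
- **The RR interval is one of the least affected items.** True. Coverage is nominal in the low scenario, half a point short in the middle one and 1.6 points short in the high one.
- **The size is all assumption, and complete pairs are hard to keep.** Each sibling must weigh under 1500 g, survive beyond 7 days and return at 2 and 6 years. This stands too. With the share in pairs halved, Mann-Whitney falls to 5.3-6.6%, uncorrected chi-square to 5.0-6.4% and corrected chi-square to 3.4-4.5%.
- **The lower power figures describe an analysis the protocol does not plan.** Correct. The planned test itself loses only about 2 points.
- **An analysis plan could deal with siblings.** This holds only in part. The interval method for the RR is left open, but Mann-Whitney is fixed for all continuous variables, so a clustered method would have to override the protocol's text.

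These points limit the size of the problem. They do not remove it.

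**Conclusion.** The concern holds. Multiples are eligible, and the procedures fixed in section 7.2 and the number in section 7 treat infants as independent. With positive sibling correlation and siblings in the same group, the direction of the error is certain; only its size is open. Under the assumed range the effect is modest. It is clearest for Mann-Whitney (5.6-8.1% instead of 5%), mild for uncorrected chi-square, near nominal for continuity-corrected chi-square, and visible in RR coverage only in the middle and high scenarios. Power for the sized comparison is not seriously harmed, although a cluster-adjusted analysis would fall somewhat below 80% in the middle and high scenarios by simulation. The conclusion rests on the inferred same-group allocation and on an assumed share of multiples and sibling correlation. This should be corrected, but it does not undermine the study.

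**What to change.** - Keep a coded pregnancy link. It can be derived from the clinical histories that section 9 allows the team to consult, within the existing deidentified coding.
- In section 7.2, cluster by pregnancy: GEE or modified Poisson regression with cluster-robust variance for relative risks, and a clustered rank test or a bootstrap that resamples pregnancies for continuous outcomes.
- In section 7, state that 90 per group assumes independent infants, and give the power of the cluster-adjusted analysis over a stated range of multiple share and ICC.

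The cost is a little linkage work, some extra analysis, and possibly software beyond the named SPSS version for the rank test or bootstrap. Under the assumed range, RR intervals become about 2-9% wider and the stated power slightly lower. No extra infants are required.
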